10.3. Recording of Adverse Events

At each contact with the subject, the investigator must seek information on adverse events by specific questioning and, as appropriate, by examination. Information on all adverse events should be recorded immediately in the source document, and also in the appropriate adverse event module of the case report form (CRF). All clearly related signs, symptoms, and abnormal diagnostic procedures results should recorded in the source document, though should be grouped under one diagnosis.

All adverse events occurring during the study period must be recorded. The clinical course of each event should be followed until resolution, stabilization, or until it has been determined that the study treatment or participation is not the cause. Serious adverse events that are still ongoing at the end of the study period must be followed up to determine the final outcome. Any serious adverse event that occurs after the study period and is considered to be possibly related to the study treatment or study participation should be recorded and reported immediately.

10.4. Reporting of Serious Adverse Events

10.4.1 IRB Notification by Sponsor-Investigator

Reports of all events (including follow-up information) that meet the definition of an unanticipated problem posing risk to subjects or others must be submitted to the IRB within one week (5 business days) following the occurrence of the unanticipated problem or the principal investigator's acquiring knowledge of the unanticipated problem in accordance with IRB policy. Additionally, the sponsor-investigator will submit a summary of all Unanticipated problems that occurred since the beginning of the study at the time of continuing review. Copies of each report and documentation of IRB notification and receipt will be kept in the Regulatory binder.

10.4.2 FDA Notification by Sponsor-Investigator

The Columbia University Medical Center Sponsor-Investigator, as holder of the IND, will be responsible for all communication with the FDA. Columbia University Medical Center Principal Investigator will report to the FDA, regardless of the site of occurrence, any adverse event that is serious, unexpected and there is evidence to suggest a causal relationship between the drug and the adverse event. These must be reported to the FDA and any affiliate sites as soon as possible, but in no case later than 15 calendar days after the sponsor determines that the information qualifies for reporting. The Sponsor-Investigator will also submit an IND annual report to the

Columbia University Medical Center Herbert Irving Comprehensive Cancer Center Version Date: 11/09/2017

FDA in accordance with 21.CFR 312.33.

The Columbia University Medical Center Sponsor Investigator must report to the FDA and any affiliate site investigators as follows:

- Any unexpected fatal or life-threatening event must be reported as soon as possible, but no later than 7 calendar days after the sponsor investigator initial receipt of the information
- Any findings from epidemiological studies, pooled analysis of multiple studies, or clinical studies, whether or not conducted under an IND, and whether or not conducted by the sponsor-investigator, that suggest a significant risk in humans exposed to the drug must be reported as soon as possible but no later than 15 calendar days after the sponsor-investigator determines that the information qualifies for reporting
- Any findings from animal or in vitro testing whether or not conducted under an IND, and whether or not conducted by the sponsor-investigator, that suggest a significant risk in humans exposed to the drug must be reported as soon as possible but no later than 15 calendar days after the sponsor-investigator determines that the information qualifies for reporting
- Any clinically important increase in the rate of a serious suspected adverse reactions over that listed in the protocol or Investigator Brochure
- Expected SAEs and AEs will be included in the IND Annual Reports.

Follow-up information to a safety report should be submitted as soon as the relevant information is available. However, if the results of a sponsor's investigation show that an adverse drug experience not initially determined to be reportable are so reportable, the sponsor investigator must report such experience as soon as possible, but no later than 15 calendar days after the determination is made.

All other serious unexpected experiences associated with the use of the study treatment will be reported to FDA as soon as possible but in no event later than 15 calendar days after initial receipt of the information.

10.4.3 DSMC Reporting by the Sponsor Investigator

Serious adverse events not constituting unanticipated problems are to be reported to the HICCC DSMC. Reporting should occur within 24 hours of knowledge of the SAE occurring at our institution or affiliate sites. CUMC will notify the HICCC DSMC within 24 hours of knowledge of the SAE once informed by the affiliate site.

Participating investigators must report each serious adverse event to the Columbia University Medical Center Overall Principal Investigator within 24 hours of learning of the occurrence using the SAE Report Form. In the event that the participating investigator does not become aware of the serious adverse event **immediately** (e.g., participant sought treatment elsewhere), the participating investigator is to report the event within 24 hours after learning of it and document the time of his or her first awareness of the adverse event. Report serious adverse events by telephone, email or facsimile to:

[name] [name]

Version Date: 11/09/2017

[contact] [contact]

Email address: CPDM [contact]

Within the following 24-48 hours, the participating investigator must provide follow-up information on the serious adverse event. Follow-up information should describe whether the event has resolved or continues, if and how the event was treated, and whether the participant will continue or discontinue study participation.

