15.10. Stopping Rules

The study may be discontinued if the study is terminated by the data and safety monitoring committee, the Food and Drug Administration (FDA), or other regulatory authorities.

Any unforeseen deaths or serious adverse events may, after a discussion between the principal investigator and investigators at other sites, prompt an interruption to study accrual pending a full investigation into the circumstances surrounding the event.

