16.3. Data and Safety Monitoring Committee

The NCI-approved Data Safety and Monitoring Committee (DSMC) of the Herbert Irving Comprehensive Cancer Center (HICCC) will monitor every subject who receives treatment on this protocol for toxicity. This protocol will adhere to the policies of the currently approved HICCC Data and Safety Monitoring Plan (DSMP), which is in accordance with NCI and CUMC-IRB policy and guidelines. The committee chair is appointed by the HICCC Director. The committee consists of HICCC faculty and staff with expertise in oncology, research pharmacy, research nursing, and data management. The DSMC convenes twice a month to review patient safety and the conduct of the trial. The PI will submit data and safety monitoring reports to the DSMC at a frequency to be determined by the DSMC based on risk to the subjects.

At the time of renewal, the study team will submit the most recent DSMC approval letter for safety review to the CUMC IRB. Any modifications that are required by the DSMC to ensure patient safety will be submitted to the IRB. All protocol deviations, violations, and eligibility waivers will be submitted to and approved by the DSMC prior to being reported to the IRB. All study data reviewed and discussed during these meetings will be kept confidential.

For multicenter research, the principal investigator will assure that there is a mechanism in place to distribute the report to all participating investigators for submission to their local IRB. The report will document that a review of data and outcomes across all centers took place on a given date. It will summarize the DSMC's review of the cumulative toxicities reported from all participating sites without specific disclosure by treatment arm. It will also inform site investigators of the study the DSMC's conclusion with respect to progress or need for modification of the protocol.

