Follow-up information is sent to the same person to whom the original SAE Report Form was sent, using a new SAE Report Form stating that this is a follow-up to the previously reported SAE and giving the date of the original report. Each re-occurrence, complication, or progression of the original event should be reported as a follow-up to that event regardless of when it occurs. The follow-up information should describe whether the event has resolved or continues, if and how it was treated, and whether the subject continued or withdrew from study participation or if study drug was interrupted or discontinued.

If the SAE is not previously documented in the Investigator's Brochure for the study drug (new occurrence) and is thought to be related to the investigational agent, the sponsor-investigator may urgently require further information from the investigator for reporting to Health Authorities.

Non-Serious Adverse Event Reporting

Non-serious adverse events will be reported to the Columbia University Medical Center Overall Principal Investigator on the toxicity Case Report Forms.

Reporting to the Institutional Review Board (IRB) and the Data and Safety Monitoring Committee:

All Unanticipated Problems (UPs) will be reported to the CUMC IRB. SAEs not constituting UPs will reported to the HICCC DSMC.

Each affiliate site will be responsible for safety reporting to their local IRB. Investigators are responsible for complying with their local IRB's reporting requirements, though must submit the required reports to their IRB no later than 7 calendar days following the occurrence of the UP or the Principal's Investigator's acquiring knowledge of the UP. Copies of each report and documentation of IRB notification and receipt must be included in the regulatory binder.

Version Date: 11/09/2017

Expected or unexpected AEs must be reported at the time of continuing review of a protocol.

Guidelines for Processing IND Safety Reports

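### The 24-hour report to the safety committee excludes serious adverse events that are unanticipated problems, and the protocol states no other expedited route for them

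*Combined protocol and SAP*

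**What the plan says.** Section 10.4.3 opens with the scope of reporting to the safety committee: "Serious adverse events not constituting unanticipated problems are to be reported to the HICCC DSMC". The clock follows: "Reporting should occur within 24 hours of knowledge of the SAE occurring at our institution or affiliate sites". For events elsewhere, "CUMC will notify the HICCC DSMC within 24 hours of knowledge of the SAE once informed by the affiliate site". Section 21.8 repeats the division for the multicentre setting: "All Unanticipated Problems (UPs) will be reported to the CUMC IRB", and then "SAEs not constituting UPs will reported to the HICCC DSMC".

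Section 10.4.1 gives UPs one week, expressed as 5 business days, to reach the IRB. Section 21.8 gives affiliate sites 7 calendar days to their local IRB. Under section 10.2 an event is a UP only if it meets all three criteria: unexpected, related or possibly related, and suggesting greater risk than previously known.

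Section 15.10 lists the DSMC, with the FDA and other regulators, among the bodies that may terminate the study. It adds that unforeseen deaths or SAEs "may, after a discussion between the principal investigator and investigators at other sites, prompt an interruption to study accrual". Section 16.3 charges the DSMC with monitoring every treated subject for toxicity and says it meets twice a month. It also says: "The PI will submit data and safety monitoring reports to the DSMC at a frequency to be determined by the DSMC".

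**The concern.** The two streams are divided the wrong way round for the committee's purpose. An SAE that is expected, or unrelated to treatment, goes to the DSMC within a day. An SAE that is unexpected, possibly related and suggestive of new risk is taken out of that stream and sent to the IRB on a slower clock. Staff who follow the text would not send such an event, for example an unexpected treatment-related death that meets all three criteria, to the DSMC as an individual expedited report.

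Section 15.10 contains no numerical toxicity boundary, so the DSMC's contribution rests on judgement about individual events and accumulating patterns. The PI is also sponsor-investigator and holder of the IND (section 10.4.2), which makes prompt independent review more valuable. What is at stake is how soon the committee learns of the events most likely to change its view of the combination's safety. The primary response analysis is not affected.

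**Working it through.** The plan gives no figure to reproduce here. The check sets the stated reporting routes side by side and then sizes the possible delay.

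**Step 1: routes and clocks.**

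| Event | Recipient | Clock | Section |
|---|---|---|---|
| SAE that is not a UP | DSMC | 24 hours | 10.4.3 (split repeated in 21.8) |
| UP | CUMC IRB | 5 business days | 10.4.1 |
| UP at an affiliate | Local IRB | 7 calendar days | 21.8 |
| Any SAE at a participating site | Overall PI | 24 hours | 10.4.3, 21.8 |
| SAE | Incyte | 24 hours | 10.4.4 |
| SAE in the safety window | Merck | generally 2 working days | 10.4.5 |
| Unexpected fatal or life-threatening event | FDA, affiliate investigators | 7 calendar days | 10.4.2 |
| Other serious, unexpected, possibly causal event | FDA, affiliate sites | 15 calendar days | 10.4.2 |
| UP | DSMC | no individual deadline | none found |

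**Step 2: how a UP does reach the DSMC.** Three periodic channels are stated:
- the Compliance Coordinator's summaries, which cover SAEs and UPs, at regularly scheduled meetings (16.4);
- remote monitoring reports, sent to the DSMC after each review, where the review includes the site's SAE and UP submissions (21.7);
- the PI's data and safety reports, at whatever frequency the DSMC sets (16.3).

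None is triggered by the event itself.

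**Step 3: size of the wait.** Inputs: DSMC meetings twice a month (16.3) and pembrolizumab on day 1 of each 21-day cycle (8.1). Assumptions: meetings are evenly spaced, about 15 days apart; each covers this trial; events occur at random between meetings; patients' infusion days are spread evenly over the cycle.
- Longest wait: about 15 days. Mean wait: 15 / 2 = 7.5 days.
- Share of on-treatment patients who reach an infusion day during a wait of w days (w no more than 21): w / 21.
- Longest wait: 15 / 21 = 0.714, about 71%.
- Mean wait: 7.5 / 21 = 0.357, about 36%.
- For a one-day notice: 1 / 21 = 0.048, about 5%.

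These shares describe what happens before the committee is told. They do not count infusions that earlier notice would have prevented, because no section says the DSMC acts within a day of notice. If this trial is not on every agenda, the wait could exceed 15 days.

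**The case against.** The strongest objection is that the protocol does not stand alone. Section 16.3 commits the study to the institutional Data and Safety Monitoring Plan. Sections 16.4 and 21.7 have monitors verify that SAEs and UPs were reported according to IRB and DSMC requirements. Those requirements are not in the documents and may include a UP deadline. This stands as a limit on the claim: one can say that the protocol states no expedited route, not that none exists. It does not rescue the wording. If an institutional rule exists, 10.4.3 and 21.8 direct staff away from it.

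It could also be argued that the 24-hour sentences in 10.4.3 refer simply to the SAE and so cover all of them. But the opening sentence fixes their scope, and 21.8 makes the same division independently, so a single slip is unlikely.

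Four stronger readings are tempting and go too far:
- **That UPs are hidden from the DSMC, or reach it by one channel only.** Three periodic channels are stated.
- **That investigators alone control whether the study pauses.** The discussion in 15.10 is one possible trigger. The same section lets the DSMC, FDA or other regulators terminate the study, and 16.3 provides for modifications that the DSMC requires. A reader might also infer that the DSMC must join every accrual pause or resume decision. That is a governance preference, and its absence contradicts nothing in the protocol.
- **That every unexpected, related SAE is diverted.** One that does not suggest greater risk than was known is not a UP and still goes to the DSMC within 24 hours.
- **That nobody learns promptly.** The overall PI and Incyte are told within 24 hours, Merck generally within 2 working days, and the FDA within 7 calendar days of an unexpected fatal or life-threatening event. This softens the consequence, but none of these recipients is the committee charged with monitoring toxicity.

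**Conclusion.** The concern holds as a defect in the stated reporting rule. Read as written, sections 10.4.3 and 21.8 give the more alarming class of SAE a slower path, with no individual deadline, to a body that can terminate the study. This is more than missing detail, because the exclusion is explicit and appears twice.

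The illustrative delay is up to about 15 days, with a mean of about 7.5. In that time up to 71% of on-treatment patients (mean about 36%) would reach another infusion day. The 71% is a worst case, for an event just after a meeting, and should not be read as typical. Both figures rest on the even-spacing and every-agenda assumptions above. The finding itself does not depend on them.

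Confidence is high about the wording. It is lower about practice, because the institutional monitoring plan was not available. The change should be made; no inferential quantity in the trial depends on it.

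**What to change.** In section 10.4.3, delete the qualifier that limits DSMC reporting to events that are not unanticipated problems, and delete the matching qualifier in section 21.8. State that all SAEs, including those that are UPs, go to the DSMC within 24 hours, and that UPs also continue to go to the IRB on the existing clock.

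Check the institutional monitoring plan before editing. If it already requires expedited reporting of UPs to the DSMC, cite that provision in both sections and align the wording with it.

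The cost is an edit to two sections. Participating sites already send every SAE to the overall PI within 24 hours, so the step adds one recipient for a small class of events. The downside is a few extra expedited notices.

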10.4.4 Reporting to Drug Manufacturer by Sponsor-Investigator (Incyte)

All Serious Adverse Events ("SAE"), including pregnancy and lactation exposure, required to be reported pursuant to the Protocol shall be provided to Incyte and its representatives by Institution or Principal Investigator within twenty-four (24) hours of learning of the event as well as any additional reports agreed upon by Institution or Principal Investigator and Incyte.

SAE Reports will be sent to: Incyte [contact].

By sending to this e-mail address, the Incyte Pharmacovigilance group will receive copies of the reports. This process will be tested and established before the first patient is enrolled in the Study. Notwithstanding anything to the contrary herein, Institution will have the primary responsibility of reporting adverse events ("AE") to regulatory authorities.

10.4.5 Reporting to Drug Manufacturer by Sponsor-Investigator (Merck)

For the time period beginning after the first dose of study treatment, any serious adverse event, or follow up to a serious adverse event, including death due to any cause that occurs to any participant must be reported within 24 hours to the Sponsor and within 2 working days to Merck Global Safety if it causes the participant to be excluded from the trial, or is the result of a protocol-specified intervention, including but not limited to washout or discontinuation of usual therapy, diet, placebo treatment or a procedure.

For the time period beginning after the first dose of study treatment through 90 days following cessation of treatment, or 30 days following cessation of treatment if the participant initiates new anticancer therapy, whichever is earlier, any serious adverse event, or follow up to a serious adverse event, including death due to any cause whether or not related to the Merck product, must be reported within 24 hours to the Sponsor and within 2 working days to Merck Global Safety.

Additionally, any serious adverse event, considered by an investigator who is a qualified physician to be related to Merck product that is brought to the attention of the investigator at any time following consent through the end of the specified safety follow-up period specified in the paragraph above, or at any time outside of the time period specified in the previous paragraph also must be reported immediately to Merck Global Safety.

All participants with serious adverse events must be followed up for outcome.

Version Date: 11/09/2017

SAE reports and any other relevant safety information are to be forwarded to the Merck Global Safety [contact]

A copy of all 15 Day Reports and Annual Progress Reports is submitted as required by FDA, European Union (EU), Pharmaceutical and Medical Devices agency (PMDA) or other local regulators. Investigators will cross reference this submission according to local regulations to the Merck Investigational Compound Number (IND, CSA, etc.) at the time of submission. Additionally investigators will submit a copy of these reports to Merck & Co., Inc. (Attn: Worldwide Product Safety; [contact]) at the time of submission to FDA.

10.4.6. Reporting Process

Adverse events may be submitted on FDA Form 3500A, the HICCC DSMC Serious Adverse Event Reporting Form, or in a narrative format. If supplied as in a narrative format, the minimum information to be supplied is noted above at the beginning of section 10.

At the time of IRB renewal or at the request of the manufacturer, the Sponsor- Investigator will submit a summary of all Serious Adverse Events that have occurred inclusive of all sites to manufacturer.

11. PHARMACEUTICAL INFORMATION

11.1. Pembrolizumab

11.1.1. Dispensing of Pembrolizumab

An initial bulk supply of pembrolizumab will be provided to investigative sites prior to enrollment of the first subject. Thereafter, the site will contact the sponsor for re-supply of pembrolizumab. The investigator or designee will calculate the number of pembrolizumab vials needed, pull the appropriate number of vials to prepare the infusion solution, and enter the vials used into the eCRF and drug accountability log. The Principal Investigator must keep accurate and up-to-date dispensation records. Any discrepancies between the amounts of Study drug dispensed and returned must also be explained in writing. All such records of drug accountability must be entered on the corresponding Subject CRF's.

11.1.2. Packaging and Formulation

Clinical Supplies will be provided by Merck as summarized in the table below

Product Name & Potency	Dosage Form
Pembrolizumab 50 mg	Lyophilized Powder for Injection
Pembrolizumab 100 mg/ 4mL	Solution for Injection

Version Date: 11/09/2017

Clinical supplies will be affixed with a clinical label in accordance with regulatory requirements.

11.1.3. Storage

Clinical supplies must be stored in a secure, limited-access location under the storage conditions specified on the label.

Receipt and dispensing of trial medication must be recorded by an authorized person at the trial site.

Clinical supplies may not be used for any purpose other than that stated in the protocol.

